1. INTRODUCTION

Bleeding during surgical procedures may manifest in many forms. It can be discrete or diffuse from a large surface area. It can be from large or small vessels; arterial (high pressure) or venous (low pressure) of high or low volume. It may be easily accessible or it may originate from difficult to access sites. The bleeding tissues may be firm or friable.

Conventional methods to achieve haemostasis include use of surgical techniques, sutures, ligatures or clips, and energy-based coagulation or cauterisation. When these conventional measures are ineffective or impractical, adjunctive haemostasis techniques and products are typically utilized, including topical absorbable haemostats such as oxidized regenerated cellulose, gelatin, or collagen and active haemostats such as topical thrombin or fibrin sealants.

Fibrin sealants are typically dual component systems consisting of virus-inactivated, human plasma-derived thrombin and fibrinogen. The two components are mixed during application to a target site and upon combination mimic the final step in the coagulation pathway to form a stable, physiological fibrin clot that assists in healingⁱ. The fibrinogen component may also contain anti-fibrinolytic agents. Fibrin sealants have proven to be valuable adjuncts for haemostasis in a variety of surgical and endoscopic procedures. They have been successfully used as biodegradable tissue adhesives for haemostasis, wound healing, or tissue sealing purposes in cardiovascular, thoracic, neurologic, gastrointestinal, urologic, gynaecologic, hepatic and plastic and reconstructive surgical procedures^{ii,iii,iv,v,vi}. They have also been evaluated in bleeding from soft tissue tumour beds following surgical resection^{vii}. Fibrin sealants have been shown to reduce post-operative complications, including blood loss and reduce the need for repeated procedures by promoting wound healing^{viii}.

The requisite preparation time for lyophilised products can be impractical and furthermore the use of fibrin sealants can complicate the application of pressure to the bleeding site, in that applied pressure can disrupt the sealant bond or cause the sealant to adhere to gloves or gauze. Application of fibrin sealants to actively bleeding sites can result in the sealant lifting or floating off the target site^{ix}, particularly in high volume or high pressure bleeding.

EVARREST Sealant Matrix/EVARREST Fibrin Sealant Patch (EVARREST) is a topical absorbable haemostat and will be evaluated in this study to measure its safety and effectiveness in controlling mild/moderate bleeding from hepatic parenchyma or soft tissue as required by the Paediatric Investigational Plan.

The Product

EVARREST is a sterile bio-absorbable combination product consisting of two constituent parts—a flexible backing and a coating of two biological components (Human Fibrinogen and Human Thrombin). The product has been developed for the management and rapid control of bleeding, including active, challenging bleeding.

The primary mechanism of action of EVARREST follows the principles of normal physiological fibrin clot formation. Upon contact with a bleeding wound surface, the biological components (Human Fibrinogen and Human Thrombin) on the matrix hydrate and the subsequent fibrinogen-thrombin reaction initiates the last step of blood clot formation in a normal and well-understood biochemical reaction. Haemostasis occurs when fibrinogen is converted into fibrin monomers, which spontaneously polymerize to a fibrin clot, forming a sealing layer that adheres to the tissue surface and integrates into the matrix. The matrix component provides physical support and a large surface area for the biological components, imparts inherent mechanical integrity to the product and supports clot formation. Natural healing occurs as the

product is absorbed by the body, which is expected to occur within approximately 8 weeks, as demonstrated in rodent and swine animal models.

The patch component of EVARREST consists of an oxidized regenerated cellulose (ORC) layer underlying a layer of polyglactin 910 (PG910) non-woven fibers. The PG910 layer contains the embedded biological components. The patch component provides a large surface area for the biological components and imparts inherent mechanical integrity to the product. The flexibility of EVARREST accommodates the physiological movements of tissues and organs.

Safety concerns potentially linked to the fibrinogen and thrombin components when used in fibrin sealants include the risks of viral transmission and anaphylactic and/or hypotensive reactions. Two independent virus inactivation/removal steps are included in the production process of each biological component of fibrin patch. These procedures ensure a high level of viral safety. As these biological components are of human origin, the risk of anaphylactic reaction should be reduced compared to fibrin sealants containing material of bovine origin.

EVARREST has been evaluated in three early phase clinical studies and five pivotal clinical studies:

1. Phase I study to evaluate the safety of the product when used adjunctively in partial nephrectomy procedures. EVARREST was used in this study as an adjunct to haemostasis (after attempts to control bleeding with conventional surgical techniques had been made).
2. Phase II study using EVARREST actively (not adjunctively) in partial nephrectomy procedures.
3. Pivotal study in 141 subjects with mild to moderate bleeding in retroperitoneal, intra-abdominal, pelvic and thoracic (non-cardiac) soft tissue conducted in US.
4. A Phase III non-IND pivotal clinical trial in 91 subjects with severe bleeding in retroperitoneal, intra-abdominal, pelvic and thoracic (non-cardiac) soft tissue conducted in Europe (UK and Germany), Australia and New Zealand.
5. A Phase III non-IND pivotal clinical trial in 104 adult subjects undergoing hepatic surgery conducted in Europe (UK, Germany, The Netherlands), Australia and New Zealand
6. A Phase II clinical trial in 42 adult subjects undergoing cardiovascular surgery conducted in the US.
7. A Phase III IND pivotal clinical trial in 102 adult subjects undergoing hepatic surgery conducted in the US, UK, Australia and New Zealand.
8. A Phase III clinical trial in 156 adult subjects undergoing cardiovascular (aortic) surgery conducted in the US, Europe (UK and Belgium), Japan and Australia.

Integrating the six randomized studies (3-8 above), of 298 randomised subjects treated with EVARREST, 89.9% achieved haemostasis at 3 or 4 minutes of randomisation and 97% achieved haemostasis within 10 minutes of randomisation. By comparison, of 267 control subjects 49.4% achieved haemostasis at 3 or 4 minutes of randomisation and 78.3% achieved haemostasis at 10 minutes.

A Phase 2 clinical study indicated that EVARREST is an effective haemostat in the clinical scenario of aortic reconstruction surgery, in systemically anticoagulated subjects on cardiopulmonary bypass, within a range of hypothermia. In the clinical setting of the study, EVARREST had a higher success rate than both TachoSil® (an Absorbable Fibrin Sealant Patch approved for use in cardiovascular surgery) and current standard of care methods in achieving immediate and durable haemostasis at the anastomotic suture line during cardiovascular surgery. No safety signals were identified during the study.

In addition, A Phase III clinical study provided additional evidence that EVARREST is safe and effective when administered with manual compression during cardiovascular surgery, wherein subjects underwent major aortic reconstruction. EVARREST was shown to be superior to TachoSil with a success rate significantly higher compared to the success rate in the TachoSil group across all efficacy time points.

The safety results showed that the incidence of clinically meaningful adverse events is evenly distributed between treatment groups and were of a nature to be expected following these surgical procedures.

2. STUDY OBJECTIVES

The objective of this study is to evaluate the safety and haemostatic effectiveness of the EVARREST versus control (SURGICEL ORC) as an adjunct to controlling mild to moderate soft hepatic parenchyma or soft tissue bleeding during open hepatic, abdominal, pelvic, retroperitoneal, and thoracic (non-cardiac) surgery in paediatric population.

The primary endpoint will be the absolute time to haemostasis, defined as the absolute time elapsed from randomisation to the last moment in time at which detectable bleeding at the TBS is observed.

The secondary endpoints of this study include:

- Proportion of subjects achieving haemostatic success at 4 minutes following randomisation and no bleeding requiring treatment at the TBS occurs any time prior to final fascial closure
- Proportion of subjects achieving haemostatic success at 10 minutes following randomisation and no bleeding requiring treatment at the TBS occurs any time prior to final fascial closure
- Portion of subjects with no re-bleeding at the TBS.
- Incidence of adverse events that are potentially related to bleeding at the TBS;
- Incidence of adverse events that are potentially related to thrombotic events;
- Incidence of re-treatment at the TBS;
- Incidence of adverse events
- Summarization of Haemoglobin, Haematocrit, Platelets laboratory results, estimated intraoperative blood loss and number of blood products transfusions

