Any EVARREST re-treatment must be performed according to the Investigator's Brochure.

All subjects will have haemostasis assessed at 10 minutes after randomisation and have absolute time to haemostasis recorded regardless of any additional treatments.

EVARREST can only be used on a single TBS to be evaluated. If additional soft tissue or hepatic parenchymal bleeding sites are identified, the surgeon should treat according to their standard of care.

TEST PRODUCT: EVARREST Sealant Matrix/ EVARREST Fibrin Sealant Patch

STUDY

POPULATION:

Paediatric subjects, undergoing non-emergent abdominal, retroperitoneal, pelvic, hepatic or thoracic (non-cardiac) surgery procedures, wherein an appropriate TBS is identified. For this study paediatric subjects for this study are defined as; Infants and toddlers (28 days (1 month) from birth to 23 months), Children (2 to 11 years) and Adolescent (12 to less than 18 years).

New born infants (0-27 days from birth) are excluded from this study. Pre-term births are excluded from this protocol until the subject reaches 28 days from 37 weeks of pregnancy as determined by the investigator.

PRIMARY

ENDPOINT: Absolute time to haemostasis defined as the absolute time elapsed from randomisation to the last moment in time at which detectable bleeding at the TBS is observed.

SECONDARY

ENDPOINTS:

- Proportion of subjects achieving haemostatic success at 4 minutes following randomisation and no bleeding requiring treatment at the TBS occurs any time prior to final fascial closure
- Proportion of subjects achieving haemostatic success at 10 minutes following randomisation and no bleeding requiring treatment at the TBS occurs any time prior to final fascial closure
- Proportion of subjects with no re-bleeding at the TBS
- Incidence of adverse events that are potentially related to bleeding at the TBS;
- Incidence of adverse events that are potentially related to thrombotic events;
- Incidence of re-treatment at the TBS;
- Incidence of adverse events
- Summarization of Haemoglobin, Haematocrit, Platelets laboratory results, volume of blood loss, & volume of blood and blood products transfusions

SAFETY:

Adverse events will be collected from time of randomisation, throughout the follow-up period. Intra-operative bleeding at the TBS after 10 minutes will be an adverse event.

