8.4 Safety

8.4.1 Safety Variables / Criteria

The following will be summarized using the Safety set:

- Incidence of adverse events that are potentially related to bleeding at the TBS;
- Incidence of adverse events that are potentially related to thrombotic events;
- Incidence of re-treatment at the TBS;
- Incidence of adverse events.
- Laboratory tests (including Haemoglobin, Haematocrit, Platelets)
- Estimated intra-operative blood loss
- Volume of blood product transfused

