3. STUDY ENDPOINTS

The primary effectiveness endpoint is absolute time to hemostasis, defined as the absolute time elapsed from randomization to the last moment in time at which detectable bleeding at the TBS is observed.

The following secondary effectiveness endpoints will be included in this study:

- Proportion of subjects achieving hemostatic success at 4 minutes following randomization and no bleeding requiring treatment at the TBS occurs any time prior to final fascial closure;
- Proportion of subjects achieving hemostatic success at 10 minutes following randomization and no bleeding requiring treatment at the TBS occurs any time prior to final fascial closure;
- Proportion of subjects with no re-bleeding at the TBS.

In addition, the following safety endpoints will be included in this study:

- Proportion of subjects with adverse events that are potentially related to bleeding at the TBS;
- Proportion of subjects with adverse events that are potentially related to thrombotic events;
- Proportion of subjects with re-treatment at the TBS;
- Incidence of adverse events;

- Hemoglobin, Hematocrit, Platelets, Volume of blood loss, Volume of blood and blood products transfusions.

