7. PROCEDURE DATA

Procedure data will be summarized descriptively for subjects in each treatment group in the FAS set. The categorical data will be summarized descriptively by frequencies along with the associated percentages. The continuous data will be presented using summary statistics such as number of subjects, mean, standard deviation, minimum, median and maximum.

The following procedure variables will be analyzed:

- Primary operative procedure;
- Operating room (OR) time;
- Procedure duration (from first incision to last suture/staple);
- Procedure duration from first incision to initiation of final fascial closure (when applicable);
- For liver resections patients: time from start of liver resection to last suture/staple and time from start of liver resection to initiation of final fascial closure (when applicable);
- Specification of treatment to which subject is randomized;
- Estimated intraoperative blood loss, blood or blood product transfusions from surgery through hospital discharge, and cell saver usage data;
- Primary method used to obtain hemostasis at the TBS;
- TBS length, width, area, and location, type of bleeding, and TBS tissue type;
- For liver only TBS: estimated total transected plane area, estimated portion of total transected plan area which is treated, reason for liver resection, type and location of resection at TBS, hepatic parenchyma classification/type and specification (if abnormal), predominant source of bleeding, type of arterial bleeding, type of venous bleeding, area of bleeding and specification (if “diffuse”);
- Approximate length and width of product applied at the TBS, TBS area, and size of EVARREST implanted (in cm^2 per kilogram of body weight);
- For patients treated with EVARREST: total number of EVARREST units used at TBS, indication of appropriate identification of TBS, presence of adequate access to TBS, indication of sufficient coverage of TBS, indication of EVARREST pads overlap at TBS, including number of overlap locations and presence of sufficient overlap, surgeon’s ability to properly apply EVARREST at its first application to TBS, and reasons for incorrect EVARREST application;
- For patients treated with SURGICEL: number of kits used at TBS and indication of SURGICEL use according to IFU;
- Hemostasis assessment data, such as time from randomization to initial application of the hemostatic product with manual compression, TBS hemostasis presence at 4 and 10 minutes from

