9. SAFETY EVALUATION

9.1 Adverse events

The following safety/secondary endpoints will be descriptively summarized using the Safety set:

- Proportion of subjects with adverse events that are potentially related to bleeding at the TBS;
- Proportion of subjects with adverse events that are potentially related to thrombotic events;
- Proportion of subjects with re-treatment at the TBS;
- Incidence of adverse events;
- Hemoglobin, Hematocrit, and Platelets, at screening, baseline, and post-surgery to hospital discharge (within 72 hours prior to discharge);
- Estimated intra-operative blood loss;
- Volume of blood and blood products transfusions (red blood cells, whole blood, fresh frozen plasma, platelets, and cryoprecipitates), intra-operatively, prior to hospital discharge, and after discharge.

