| 3.1.6 | Summary of during/post treatment study treatment related (possibly, definitely) adverse events by patient and coded terms – Safety analysis set | Includes adverse events for which the answer for CRF item “Relationship to study treatment” is “Possibly related” or “Related”. | AM |
| 3.2 | Laboratory data | Reported in SI units | |
| 3.2.1 | Laboratory data: Full Blood Count - Safety analysis set | At screening, at baseline, and post-surgery to hospital discharge - within 72 hours prior to discharge) | L |
| 3.2.2 | Laboratory data: White Blood Cell Differential - Safety analysis set | At screening, at baseline, and post-surgery to hospital discharge - within 72 hours prior to discharge) | L |
| 3.2.3 | Laboratory data: Coagulation Parameters - Safety analysis set | At screening, at baseline, and post-surgery to hospital discharge - within 72 hours prior to discharge) | L |
| 3.3 | Other safety data | | |
| 3.3 | Safety/secondary endpoints – Safety analysis set | Proportion of subjects with adverse events that are potentially related to bleeding at the TBS, proportion of subjects with adverse events that are potentially related to thrombotic events, proportion of subjects with re-treatment at the TBS (all d), estimated intra-operative blood loss (mL) (c), and volume of blood and blood products transfusions (red blood cells, whole blood, fresh frozen plasma, platelets, and cryoprecipitates), intra-operatively, prior to hospital discharge, and after discharge (all c) | G2 |

Note: ‘–’ indicates a new line in the title.

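### Blood loss and transfusion volume are summarised without body-weight scaling across ages 28 days to under 18 years, which adds avoidable noise to the descriptive safety tables

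*Protocol*

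**What the plan says.** **Unit and scaling.** SAP Table 14.3.3 lists "estimated intra-operative blood loss (mL) (c), and volume of blood and blood products transfusions". Table 14.1.3.1 also gives intra-operative blood loss in mL, with a yes/no indicator of any transfusion. Neither these tables nor SAP 9.1 scale anything by weight. Under SAP 10.2, continuous variables get mean, SD, minimum, median and maximum.

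**Weight.** Protocol 7.1.2 has weight recorded at baseline, and SAP 6.1 lists it as a demographic variable by arm. The SAP scales one quantity by weight: "size of EVARREST implanted (in cm^2 per kilogram of body weight" (SAP 7).

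**Age bands.** SAP 8.2 gives age-group summaries for the primary endpoint only. Protocol 8.3.2 has a general split at 1 year, but within the effectiveness methods, and it keeps 1 to under 18 years together. The three-band split in protocol 8.4.2 is for adverse events.

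**Wording.** Protocol section 2 has "estimated intraoperative blood loss and number of blood products transfusions". The synopsis has "volume of blood loss, & volume of blood and blood products transfusions", protocol 8.4.1 has "Volume of blood product transfused", and SAP 3 has "Volume of blood loss, Volume of blood and blood products transfusions". The synopsis and SAP 3 set no period for blood loss. Protocol 2 and 8.4.1, SAP 9.1 and both tables restrict it to the operation.

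**The concern.** A given bleed per kilogram is a very different volume in an infant and an adolescent: 10 mL/kg is 40 mL at 4 kg and 600 mL at 60 kg. An arm mean in mL therefore depends partly on how many heavier children the arm happened to receive. Allocation is plain 1:1, and no stratification by age or weight is described in protocol 5.2 or SAP 2, so with about 20 per arm the weights can differ noticeably by chance.

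No test of these variables is planned, so readers will judge bleeding safety from the descriptive figures themselves. A chance weight difference can then look like a bleeding difference, or hide one. The SAP already recognises that patch area needs scaling, and the same variable would serve here.

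**Working it through.** **No figure to reproduce.** The 40 subjects come without a formal calculation (protocol 8.1, SAP 8.2.1). The documents give no SD of weight, blood loss or transfusion volume.

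**What the documents imply about weight.** One large unit is 10.2 x 10.2 = 104.04 cm². At the protocol's 6.9 cm²/kg, one unit corresponds to 104.04 / 6.9 = 15.1 kg and four units to 416.16 / 6.9 = 60.3 kg. The protocol thus provides for at least a fourfold weight range, before counting infants. This uses the limit only as a weight anchor and implies nothing about the limit itself.

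**Assumptions (not in the documents).** 36 children log-uniform over 9-70 kg; 4 infants log-uniform over 4-10 kg; 20 per arm; no treatment effect; volume = weight x loss per kg, the two independent; loss per kg lognormal with CV 50%, 100% or 150%; no zeros.

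**Variance.** On the log scale, Var(mL) = Var(log weight) + Var(log loss per kg).
- Within the older group: (ln 70/9)² / 12 = 0.351. Within infants: (ln 10/4)² / 12 = 0.070.
- Between groups: 0.9 x 0.1 x (3.223 - 1.844)² = 0.171.
- Var(log weight) = 0.9 x 0.351 + 0.1 x 0.070 + 0.171 = 0.494.
- Var(log loss per kg) = ln(1 + CV²) = 0.223, 0.693 and 1.179.
- Variance in mL relative to mL/kg: 0.717/0.223 = 3.2, 1.187/0.693 = 1.7 and 1.673/1.179 = 1.4.
- Share due to weight: 69%, 42% and 30%.

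**Chance of a spurious 1.5-fold difference in arm means, either direction** (40,000 simulated trials per scenario):

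| CV of loss per kg | mL | mL/kg |
|---|---|---|
| 50% | 14% | 1% |
| 100% | 32% | 18-19% |
| 150% | 44% | 35% |

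At CV 50% the 95% range of the arm-mean ratio is about 0.58-1.72 in mL and 0.73-1.36 in mL/kg.

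**Sensitivity.**
- Older children 12-50 kg: 8% against 1% at CV 50%, and 27% against 18-19% at CV 100%.
- Medians instead of means (9-70 kg, CV 50%): 25% against 3%, so the planned median does not remove the problem.
- Uniform weights over 10-65, 15-60 or 8-80 kg, with infants as one tenth, and SD of log loss per kg from 0.4 to 1.0: weight is 28-79% of log-variance. The mean weights of two arms of 20 differ by more than 20% in 21-31% of trials.
- Zeros, relevant to transfusion: with 70% of subjects at zero, the rates are about 58-59% against 49-50% (CV 50%) and 66% against 60% (CV 100%).

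**The case against.** A reader might infer that raw volumes cannot be compared between arms, or that weight swamps any treatment difference. The documents do not support either. Randomisation makes weight a source of variance and chance imbalance, not of systematic bias. At CV 100% weight is already a minority of the log-variance, and a large true difference would still show in mL.

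A reader might also infer that excess bleeding in small children would be invisible. That goes too far. Weight is tabulated by arm, the listings cover all data on the database (SAP 10.3), haemoglobin and haematocrit are reported, and intra-operative bleeding at the target site after 10 minutes counts as an adverse event. An overall mL/kg mean would still dilute an excess confined to the four infants.

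Three further points stand:
- SAP 9.4 rules out inference on safety variables, so what suffers is interpretation and not a test.
- Intra-operative blood loss, as worded, covers the whole operation, including dissection before randomisation and other bleeding sites. It is a weak measure of treatment effect on either scale.
- Bleeding is mild or moderate, so many children may need no transfusion. Mean transfusion volume is then uninformative on either scale, and the planned yes/no indicator is more useful.

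These points limit the size of the matter. They do not give a reason to omit the scaled summary.

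The count in protocol section 2 might be read as leaving the endpoint undefined. It does not: the synopsis, protocol 8.4.1 and the SAP agree on volume, so it is a wording slip.

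**Conclusion.** The point holds as one of avoidable imprecision in descriptive safety tables. Under the main weight assumptions, scaling cuts the chance of a misleading 1.5-fold difference in mean blood loss from about 14% to 1% at CV 50%, from 32% to about 19% at CV 100%, and from 44% to 35% at CV 150%. The direction was the same in every scenario examined, but the size depends on assumed weights, proportionality of loss to weight, and no zeros. The benefit shrinks as loss per kg becomes more variable, and is smaller for transfusion volume if many values are zero. No bias and no failed analysis is implied. The number/volume difference and the varying blood-loss period are minor wording matters.

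**What to change.** **SAP (free improvement).** In SAP 9.1 and Tables 14.1.3.1 and 14.3.3, add blood loss and transfusion volume in mL per kg of baseline weight, with mean, SD, median, minimum and maximum. Keep raw mL and the yes/no transfusion indicator beside them. This takes one derivation per variable from data already collected and changes neither study conduct nor sample size. The endpoints need no redefinition, and raw mL should stay in the tables.

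**Wording.** Align protocol section 2 with the synopsis, protocol 8.4.1 and the SAP on volume, and state one period for blood loss throughout. Protocol 12.1 requires amendments to go to the regulatory authorities, IRBs and ethics committees, so the protocol correction is best carried with the next amendment. The mL/kg rows need only the SAP and need not wait for it.
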